1. INTRODUCTION

Obesity is a significant public health concern. Nearly two-third of US adults are overweight or obese (body mass index [BMI] ≥ 25 and ≥ 30 kg/m², respectively).¹ It is well known that excess body weight is associated with increased risk for a number of chronic conditions including diabetes, heart disease, and some cancers including colorectal cancer (CRC).

Effective dietary strategies are essential to address the issues of obesity and related metabolic disorders. Diet composition is one factor that could influence dietary energy intake. For example, diets that are high in fiber require more chewing and a greater volume is consumed at a given energy intake (kcal/g). These factors could lead to earlier termination of eating and increased satiation. In addition, fiber-rich diets may impact physiological mechanisms important for weight control including hormone release and gastric emptying.^{2,3}

Epidemiologic research has linked higher legume consumption with reduced risk for obesity² and in some studies, with reduced risk for CRC and the precursor lesions, adenomatous polyps.⁴ In previous research that targeted men at increased risk for CRC we observed that a high-legume diet provided under conditions of weight maintenance favorably influenced biomarkers of inflammation, lipid levels, and gut hormone concentrations.⁵⁻⁹ In the same study, during a 4-week ancillary diet period where participants consumed the full legume diet entrée but with side dishes ad libitum and were allowed to lose weight, the high-legume diet facilitated weight loss.⁸ Participants consumed less total energy (-770 kcal/d below requirements for weight maintenance), lost weight (-4.0 kg; -4.4%) and serum lipid and gut hormone concentrations and biomarkers of insulin sensitivity (plasma glucose: -5.7%; insulin: -15.8%; serum C-peptide: -17.4%) and inflammation (serum CRP: -20.2) all improved significantly. This sub-study was conducted after an intensive 12 week randomized controlled crossover feeding trial but the sub-study itself was not randomized and controlled. We did not have the resources needed to conduct a feeding response time-course experiment or to explore other novel mechanisms through which legumes may facilitate weight loss (e.g. appetite-regulating hormones, gastric emptying and transit time). In addition, the provision of all of the diet components may have played a role in controlling intake and promoting weight loss.

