1.1.2. Secondary Objectives

1. Assess whether the legume diet reduces the average daily dietary energy intake of participants compared to a controlled diet.
2. Compare satiety of the high-legume diet to the control diet using self-reported satiety questionnaires.
3. Assess the effects of the two diet treatments on fasting levels of C-reactive protein (CRP, a marker of inflammation) and total cholesterol level.
4. Evaluate the effects of the aforementioned diet treatments on markers of appetite regulation (cholecystikinin – CCK) and insulin resistance (insulin, glucose) in a meal response time course experiment.
5. Compare the effects of the high-legume and control diets on gastric emptying time and gut transit time.
6. Evaluate diet-related changes in fecal biomarkers associated with CRC risk.

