3.1.1. Timing of Biological Specimen Collection

At randomization, after a one week run-in period, the baseline blood and fecal samples will be collected. These same specimens will be also collected at the end of the study period, after 8 weeks. All biomarker collections will take place at the Emory ACTSI site.

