4.1.5. Blood Collection

Approximately 70ml of blood will be collected from the subjects at each of two time points at randomization and at the end of the eight week diet period. Samples will be collected after an overnight fast and in the early morning. For satiety measures, 15 ml of blood will be drawn before the test meal (fasting), and 10 ml of blood at 5 time points thereafter (30, 60, 90, 120, and 180 minutes). Serum and plasma samples will be aliquoted in smaller vials and frozen at -70°C and stored for analysis at the completion of the study.

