Within-subject changes in end-points will be compared by paired t-test; comparisons between treatment groups by two-sample t-tests. For the time course experiments, because of the large expected individual variations in fasting levels of metabolic and appetite hormones, we intend to compute the change from baseline at each time point for each individual for all of the variables and subsequently comparing the area under the curve results⁵⁵. All data will be presented as means \pm SEM; the probability level at which differences will be considered significant will be $P < 0.05$. All analyses will be performed using the most recent version of SAS (SAS Institute, Cary, NC).

Timeline

	Mo. 1	Mo. 2	Mo. 3	Mo. 4	Mo. 5	Mo. 6	Mo. 7	Mo. 8	Mo. 9	Mo. 10	Mo. 11	Mo. 12
IRB Approval, set up	X	X										
Recruiting			X	X	X	X	X	X				
Follow-up				X	X	X	X	X	X	X		
Biomarker Analysis									X	X	X	X
Statistical Analysis											X	X
Manuscript Preparation											X	X
Report to Funding Agency												X
Draft of Subsequent R01												X

REFERENCES

1. National Center for Health Statistics (NCHS). National Health and Nutrition Examination Survey Data. 2005-2006. *US Dept. of Health and Human Services, Centers for Disease Control and Prevention*. 2007; Washington, DC.

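### The time-course AUC most naturally subtracts each visit's fasting value, so a diet-related fall in fasting glucose (less so insulin) can be hidden or read as a worse response

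*Combined protocol and SAP*

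**What the plan says.** Section 4.2 (Statistical Considerations) gives one rule for the time-course data: "compute the change from baseline at each time point for each individual for all of the variables", followed by a comparison of the areas under the curve. The reason given is "because of the large expected individual variations in fasting levels of metabolic and appetite hormones". That reason points to the pre-meal sample as the value subtracted, but the section does not say so. Section 3.1.1 uses the same word for the randomisation visit, when "the baseline blood and fecal samples will be collected".

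Section 4.1.5 sets two visits: "Approximately 70ml of blood will be collected from the subjects at each of two time points at randomization and at the end" of the diet period. At each, "15 ml of blood will be drawn before the test meal (fasting), and 10 ml of blood at 5 time points thereafter (30, 60, 90," with the list continuing to 120 and 180 minutes.

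Secondary objective 4 (section 1.1.2) uses the curves for CCK and for "insulin resistance (insulin, glucose) in a meal response time course experiment". Objective 3 names fasting endpoints, but only CRP and total cholesterol. Section 4.2 compares the arms by two-sample t-tests, with no covariate. The Introduction reports changes on the legume diet in an earlier sub-study: "plasma glucose: -5.7%; insulin: -15.8%; serum C-peptide: -17.4" percent.

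**The concern.** If baseline is that visit's fasting sample, the rule produces an incremental AUC. At randomisation this is harmless. At week 8 the fasting value has been measured after eight weeks on the assigned diet, so subtracting it removes part of any diet effect on glucose or insulin level.

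A lower fasting glucose or insulin bears directly on insulin resistance, which is what objective 4 sets out to measure. No fasting glucose, fasting insulin or total-AUC comparison is named that would pick it up. The pilot could then report no effect, or an apparent worsening, when levels had fallen. Section 4.2 also intends the secondary outcomes to inform the sample size of a full-scale trial, so a misleading effect size would be carried forward.

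**Working it through.** The plan states no AUC value or AUC power, so there is no figure to reproduce.

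**Inputs from the documents.** Sampling times 0, 30, 60, 90, 120 and 180 min (section 4.1.5). Earlier changes of -5.7% for glucose and -15.8% for insulin (Introduction).

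**Assumptions, because the documents give no absolute levels.** Three illustrative curves per analyte at those six times:
- Glucose, mg/dL: 100, 120, 118, 112, 106, 100; 100, 140, 135, 122, 112, 100; 100, 165, 160, 145, 130, 110.
- Insulin, µU/mL: 12, 45, 42, 33, 25, 15; 12, 70, 65, 50, 38, 20; 15, 110, 100, 80, 60, 30.

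**Step 1: weights.** The trapezoid weights are 15, 30, 30, 30, 45 and 30 min, which sum to 180. Write y0 for the fasting value.

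Incremental AUC = total AUC - 180 × y0

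The fasting sample therefore carries 15 - 180 = -165 min in the incremental AUC, and the five post-meal samples together carry +165 min.

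**Step 2: a fasting-only fall in glucose.** 5.7% of 100 is 5.7 mg/dL. The incremental AUC rises by 165 × 5.7 = 940.5 mg·min/dL. With a mean post-meal increment of 30 mg/dL, the starting incremental AUC is 165 × 30 = 4,950, and 940.5 / 4,950 = 19%. For mean increments of 50 and 20 mg/dL the rise is 5.7/50 = 11% and 5.7/20 = 29%.

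**Step 3: other patterns.** The fasting value falls by 5.7% (glucose) or 15.8% (insulin) in every row. Ranges are across the three curves.

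| Post-meal change | Glucose, total | Glucose, incremental | Insulin, total | Insulin, incremental |
|---|---|---|---|---|
| Same absolute fall | -4.1% to -5.2% | 0.0% | -3.4% to -6.4% | 0.0% |
| Half the absolute fall | -2.2% to -2.8% | +7% to +27% | -1.8% to -3.5% | +2% to +5% |
| None | -0.3% to -0.4% | +14% to +53% | -0.3% to -0.5% | +4% to +10% |
| Half the percentage fall | -3.0% to -3.1% | +4% to +24% | -8.0% to -8.2% | -3% to -6% |
| Same percentage fall | -5.7% | -5.7% | -15.8% | -15.8% |
| Twice the absolute fall | -7.9% to -9.9% | -14% to -53% | -6.5% to -12.2% | -4% to -10% |

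**Step 4: break-even.** The incremental AUC is unchanged when the mean post-meal fall equals the fasting fall in absolute units.
- Glucose: 5.7 against weighted mean post-meal levels of 110.7 to 140.9 mg/dL, a post-meal fall of 5.1% to 4.0%. This is close to the 5.7% fasting fall, so modest departures from proportionality hide or reverse the effect.
- Insulin: 1.896 (15.8% of 12) against 31.4, and 2.37 (15.8% of 15) against 74.5, a post-meal fall of 6.0% to 3.2%. Post-meal insulin would have to fall far less than the 15.8% fasting fall.

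**Step 5: between arms.** The distortion relative to total AUC is -180 × (fasting change on legume - fasting change on control). If, as an assumption, control fasting glucose fell by half as much (2.85 mg/dL), the fasting-only figure in Step 2 would become 165 × (5.7 - 2.85) = 470 mg·min/dL. The within-arm paired tests face the full fasting change.

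**The case against.** **Baseline may mean the randomisation visit.** If so, a fasting fall stays in the week-8 AUC and the problem disappears. The word is open. The stated reason, variation in fasting levels, favours the pre-meal reading, and an undefined term that lets the same data give different answers needs fixing on either reading.

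**The incremental AUC is a valid summary of a meal response, and objective 4 is a meal-response experiment.** This stands. A reader might infer that total AUC should simply replace it, and the documents do not support that. The gap is that it is the only named analysis for markers labelled insulin resistance. The fasting samples are drawn and assayed, so the data exist, but no comparison of them is specified.

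**The earlier data do not show a fasting fall against control.** This also stands. The Introduction does not label its glucose and insulin changes as fasting, the sub-study had no randomised comparator, and it came with a 4.0 kg weight loss. Section 2.2.1 plans weight loss for every participant, so fasting values may fall in both arms.

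**Precision.** A reader might infer that subtraction makes the endpoint much noisier. If each sample has independent error variance S, the time-averaged variances are 0.181S for total and 1.014S for incremental AUC, a ratio of 5.6. That leaves out the shared level variation T that section 4.2 gives as its reason for subtracting. With it, total AUC has variance T + 0.181S, and subtraction is the less variable choice at a single visit once T exceeds 0.833S. The documents give neither quantity, so no precision claim is made here.

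**Conclusion.** The point holds as a conditional risk, if baseline is each visit's fasting sample. An equal absolute fall then shows as exactly zero change, and a smaller post-meal fall shows as a rise. The 940 mg·min/dL (19%, or 11% to 29% across the assumed increments) is an upper case: it assumes no post-meal change and no fasting change on control. The percentages rest on assumed curves; the identity in Step 1 does not.

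The risk is material for glucose. It is weaker for insulin, where the incremental AUC still falls if post-meal levels drop by half the fasting percentage. A reader might extend it to CCK, but the documents expect no fall in fasting CCK, and section 1.2.6 states its hypothesis for post-meal levels. Nor do the documents support saying that the diet effect will be reversed: a proportional fall remains fully visible.

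**What to change.** 1. State in section 4.2 that baseline in the AUC rule is the pre-meal sample of the same visit.
2. Replace the unadjusted two-sample t-test on AUC with an ANCOVA of the week-8 AUC by arm, adjusted for the same man's randomisation-visit AUC. This handles stable variation between men with a pre-randomisation value.
3. For glucose and insulin, report total AUC 0-180 min and the fasting value by arm beside the incremental AUC, and draw no conclusion on insulin resistance from the incremental AUC alone.
4. Keep the incremental AUC for CCK.

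No new samples or visits are needed. The covariate costs one degree of freedom: with all 14 men, residual degrees of freedom go from 14 - 2 = 12 to 14 - 3 = 11. The other cost is a few more secondary results to report, which should be labelled as exploratory in a pilot of this size.

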1.1. Study Objectives

This pilot randomized trial will evaluate the effects of diet composition, comparing a legume-rich diet and a control diet, on weight loss over the course of eight weeks. The primary outcome is weight loss. Secondary objectives will compare the effects of the two diets on total energy intake, biomarkers related to appetite regulation and blood glucose control and in exploratory

analyses will assess other aspects related to weight loss (e.g., effects on gastrointestinal emptying and transit time and on gut microbiota).

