4.2. Statistical Considerations

The main endpoint of interest in this study is weight loss. There are several proposed mechanisms by which legumes are thought to promote weight loss, many of which have not been tested in a controlled setting. Due to new technology, we are now able to examine one of these proposed mechanisms—colon transit time, allowing us to directly observe a legume diet's physiologic effect. Previous studies of legume-heavy diets have shown indications that the particular type of fiber specific to legumes may increase satiety and slow gastric emptying significantly, leading patients to consume fewer calories per day, thereby promoting weight loss without intensive intervention from the study staff. Thus, we do expect to have differences in energy intake between groups. The analyses will follow the intent-to-treat principle. BMI will certainly be considered as a possible confounder. Since this is a pilot trial, doing so will be important to determine the appropriate target population for a full-scale trial and whether randomization in that protocol should be stratified by BMI. Secondary outcomes, including both the satiety hormones and glucose are expected to rise quickly in response to the test meal and then decline over the course of the next few hours as gastric emptying occurs.

In the Legume Inflammation Feeding Experiment full-feeding study, participants averaged -3.9 ± 0.4 kg over the course of four weeks⁸. Ten participants (five individuals per treatment arm) would be sufficient to detect a difference of just 1.25kg (we expect > 1 kg) in weight loss, with 80% power, assuming a standard deviation for each groups' weight loss that is slightly higher (± 0.7 kg) than seen in our prior study⁸. To account for the potential small dropout rate, we will recruit a total of 14 patients (7 per treatment arm). There are multiple secondary outcomes that we are interested in determining the appropriate sample size for when we run a full-scale study. Some of these outcomes are novel, so we are exploring the feasibility of pursuing them in a full scale study.

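### One P < 0.05 rule covers about 7 to 10 secondary outcomes in a 14-man pilot; estimates with 95% confidence intervals would serve its planning aim better

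*Combined protocol and SAP*

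**What the plan says.** Section 1.1 names one primary outcome: "The primary outcome is weight loss". Section 1.1.2 then lists six secondary objectives. The first three read "Assess whether the legume diet reduces the average daily dietary energy intake of participants", "Compare satiety of the high-legume diet to the control diet using self-reported satiety questionnaires", and effects on "fasting levels of C-reactive protein (CRP, a marker of inflammation) and total cholesterol level". The other three cover CCK, insulin and glucose after a test meal, gastric emptying and gut transit, and fecal markers of CRC risk. That makes at least 10 outcomes.

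Section 4.2 gives one analysis rule for everything. "Within-subject changes in end-points will be compared by paired t-test"; "comparisons between treatment groups by two-sample t-tests"; and "the probability level at which differences will be considered significant will be" P < 0.05. Data are shown as means ± SEM. There is no ordering of outcomes, no multiplicity adjustment, no confidence interval, and no statement that secondary p-values are descriptive.

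The same section gives the purpose of these outcomes: "There are multiple secondary outcomes that we are interested in determining the appropriate sample size for when we run a full-scale study". It describes some of them as novel and under test for feasibility. Recruitment is 14 men, 7 per arm, with 5 per arm taken as sufficient for the weight comparison.

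**The concern.** With 5 to 7 men per arm, a secondary outcome reaches P < 0.05 only if the observed difference is very large. Two things follow. Testing many outcomes at the same level gives a substantial chance that at least one is called significant when nothing differs. And where a true effect is small or moderate, the pilots that reach significance are those in which chance enlarged the difference.

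This matters because the pilot is meant to inform a larger trial. A significance label on one or two of ten outcomes invites readers to treat those outcomes, and their observed differences, as established. If outcomes were chosen or sized that way, the next trial would be too small. A difference, a confidence interval and an SD for every outcome would give the planning information directly.

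**Working it through.** **Inputs.** From section 4.2: 7 per arm recruited, 5 per arm needed, level 0.05, difference 1.25 kg, SD 0.7 kg, power 80%. From section 1.1.2: at least 10 secondary outcomes. Assumed: two-sided tests (sidedness is not stated), normal outcomes, equal variances. The documents give no secondary effect sizes or correlations, so ranges are used.

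**1. The plan's own figure.** n per arm = 2 × (1.96 + 0.8416)² × (0.7/1.25)² = 2 × 7.849 × 0.3136 = 4.92, rounded up to 5. This matches the plan. The normal approximation gives 80.6% power at 5 per arm; the exact t calculation gives 69.7% at 5 and 86.5% at 7. The primary test is not at issue in this point.

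**2. Number of secondary outcomes.** Energy intake, satiety, CRP, cholesterol, CCK, insulin and glucose make 7. Gastric emptying, gut transit and fecal markers bring the total to at least 10. The last three are debatable: section 1.1 calls emptying, transit and microbiota exploratory, and section 4.1.9 stores stool for later analysis.

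**3. Chance of at least one false positive, between-arm tests, all nulls true.**
- 10 independent tests: 1 − 0.95^10 = 40.1%.
- 7 independent tests: 1 − 0.95^7 = 30.2%.
- 10 tests with equal correlation (simulated): about 36% at 0.3, 30% at 0.5 and 23% at 0.7.

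Counting the planned paired tests in each arm as well (30 tests) gives about 71% at correlation 0 and 47% to 49% at 0.7. I do not rely on that. It requires no true change within either arm, yet section 2.2.1 plans an energy deficit for every participant.

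**4. Smallest observed difference that can be significant.** d = t(0.975, 2n − 2) × √(2/n).
- 7 per arm: 2.179 × 0.5345 = 1.16 SD.
- 5 per arm: 2.306 × 0.6325 = 1.46 SD.

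No assumption about the true effect enters here.

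**5. Average overstatement given significance.** This is the mean absolute raw difference among significant results, divided by the true difference (simulated, 1,000,000 runs per row).

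| True effect (assumed) | Power, 7 per arm | Overstatement, 7 per arm | Overstatement, 5 per arm |
|---|---|---|---|
| 0.2 SD | 6% | 6.0× | 6.7× |
| 0.5 SD | 14% | 2.6× | 2.9× |
| 0.8 SD | 28% | 1.7× | 2.0× |
| 1.0 SD | 41% | 1.5× | 1.7× |
| 1.79 SD (= 1.25/0.7) | 87% | 1.07× | 1.15× |

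**6. What would follow if an observed significant difference were used for sizing.** The plan does not say that it will be. With n per arm = 2 × 7.849/d², the smallest significant difference at 7 per arm gives 15.70/1.1646² = 11.6, so no significant outcome could lead to more than 12 per arm. A true effect of 0.5 SD needs 15.70/0.25 = 62.8, so 63 per arm.

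**The case against.** The strongest reply is that this is a pilot with one named primary outcome, and that unadjusted secondary tests are acceptable in a pilot if treated as exploratory. Sections 1.1 and 4.2 partly frame them so. This stands as an argument against requiring a multiplicity correction, and none is proposed here. It does not fill the gap: the exploratory and feasibility wording reaches only some outcomes, while the significance rule reaches all.

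A second reply is that the harm needs a step the plan does not contain. A reader might infer that outcomes will go forward because they reached P < 0.05, or that observed differences will size the next trial. The documents say neither. The one sample-size calculation they contain uses an SD based on prior work and a difference named in advance. SDs can also be recovered from means ± SEM, and testing does not distort them as long as every outcome is kept. This reply stands, so the harm to the next trial is conditional. One qualification: among significant results only, the SD is also biased low. At a true 0.5 SD its median is about 0.76 (5 per arm) or 0.85 (7 per arm) of the true value.

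Two stronger readings also fail. A false positive is not more likely than not: 40% is the figure for 10 independent tests with every null true, and it falls with correlation or a shorter list. Passing 50% would take 14 independent outcomes (1 − 0.95^14 = 51%), and the plan does not list 14. Nor is every significant effect several times too large: for true effects of 1 SD or more at 7 per arm, the average overstatement is 1.5 times or less.

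**Conclusion.** The point holds as a cheap improvement. The stated rule would attach the label significant to any of about 7 to 10 secondary outcomes in 14 men, with a 23% to 40% chance of at least one false-positive between-arm result if nothing truly differs. The lower end rests on an assumed correlation of 0.7, the upper on 10 independent tests. The thresholds of 1.16 and 1.46 SD depend only on the sample size, the level and a two-sided test. The overstatement, from about 6 times at 0.2 SD to about 1.1 times at 1.8 SD with 7 per arm, depends on true effects that the documents do not give. The false-positive and overstatement figures describe different situations (no effect and some effect) and should not be combined for one outcome. Damage to the full-scale trial would arise only if significance or observed differences were used to choose or size its outcomes, which the plan neither states nor rules out.

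**What to change.** In the analysis paragraph of section 4.2:

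- Reserve the P < 0.05 rule for the between-arm comparison of weight loss.
- Report each secondary outcome as a between-arm difference with a 95% confidence interval, labelled exploratory.
- State that the full-scale trial will be sized from the pilot SD, with its uncertainty, and a worthwhile difference set in advance, as section 4.2 already does for weight. Outcomes should not be picked because they reached P < 0.05.

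The uncertainty in the SD deserves a line of its own. With 12 degrees of freedom (7 per arm), the 95% interval for the true SD runs from √(12/23.34) = 0.72 to √(12/4.40) = 1.65 times the observed value. The required sample size scales with the square of the SD, so it runs from about 0.5 to 2.7 times the point figure.

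The cost is a few sentences. No extra participants or measurements are needed, and the primary test is unchanged. The downside is fewer statements of significance in the report.
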